### **6.10.2 Prior, Concomitant, and Newly Initiated Medications**

Prior medications and concomitant medications will be extracted from the Prior/Concomitant Medication CRF. Medications taken prior to Study Day 1 will be considered as prior medications, medications taken on or after Study Day 1 will be considered as concomitant medications, and newly initiated medication refers to any medication with a start date  $\geq$  Study Day 1. We note that a prior medication may also be a concomitant medication if the start date is prior to Study Day 1 and the end date is on/after Study Day 1. Medications will be coded using WHO Drug Dictionary (WHODD March 2018 release) for PT and Anatomical Therapeutic Chemical (ATC) classification.

Medications will be tabulated separately based on the Safety population. The number (n and %) of subjects taking at least 1 medication and the number (%) of subjects taking each medication at the PT level will be tabulated by ATC4 and PT. Subjects taking the same PT medication twice will only be counted once.

A subject data listing will be provided to include the reported medication name, the WHODD PT, ATC4, study day, and pertinent subject information.

A separate data listing will include subjects who have received prohibited medications.

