- 33) If absolute lymphocyte and/or eosinophil counts do not recover (to normal range or baseline levels) by Day 197 (or ET), extended follow-up visits are required every 28 (± 3) days) to monitor blood counts until they recover. Extended follow-up visits consist of blood collection for CBC with differential and collection of AESI and SAE.
- 34) After completion of the Day 169 visit, the Investigator will evaluate whether the subject is eligible for the OLE period. If the subject is eligible, the subject will be given the option to participate in the OLE period beginning approximately 1 week after the Day 169 visit. Approximately 1 week after the Day 169 visit (on Day 176 ± 3 days), eligible subjects that choose to participate in the OLE period will begin following the OLE Schedule of Events (Table 5) and will receive the first open-label AK002 infusion. For subjects participating in the OLE period, AE and concomitant medications should be collected and recorded in the AK002-014 Treatment Period database up until the start of the first open-label infusion during the Day 176 visit. This includes prednisone premedication administered prior to the Day 176 visit of the OLE period, which should be recorded in the Concomitant Medications CRF of both the AK002-014 treatment period database and the AK002-014 OLE period database.
- 35) Sites should strive to conduct visits within a ± 3 day window, but visits conducted within ± 7 days are acceptable and are not considered deviations. Visits conducted ± 4 -7 days from the target visit date should be minimized as much as possible. Any visit conducted outside of the ± 3 day window should receive prior written approval from Allakos.

6. Criteria for Evaluation

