6.1 Safety Endpoints

The safety and tolerability of AK002 will be assessed by determining the following:

- Physical examination (Section 11.3.5, 11.3.6)
- Changes in vital signs (Section 11.3.4)
- Changes in Hematology (Section 11.2.8 and Section 11.4.1)
- Changes in Blood chemistry (Section 11.4.2)
- Changes in Urinalysis (Section 11.4.3)
- Anti-drug antibodies (Section 11.4.7)
- Treatment-emergent adverse events (Section 13) include severity, withdrawals due to AE, and other safety parameters.
- Changes in concomitant medications beginning on or after the first infusion of study drug (Section 11.3.1)

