Prior and concomitant medications (which include both prescribed and over-the-counter medications taken at any point beginning 30 days prior to the screening visit and until the end of study participation) will be recorded in the electronic Case Report Forms (eCRF). For subjects participating in the OLE period, concomitant medications should be recorded in the AK002-014 treatment period database up until the first open-label dose is administered during the Day 176 visit. This includes the prednisone premedication administered prior to the Day 176 visit in the OLE period, which should be recorded in the Concomitant Medications CRF of both the AK002-014 treatment period database and the AK002-014 OLE period database.

Subjects should be advised against taking any new medication or modifying the dose of existing medication, both prescribed and over the counter, without consulting the Investigator, unless the new medication or change in dose is required for emergency use. Immediately prior to the first infusion, study site personnel should ensure that the subject continues to meet the inclusion criteria and none of the exclusion criteria including no use of prohibited medications. All medications taken for the 30 days before screening and during participation in this study must be documented on the eCRF. All medications used to treat IRR or AE must also be documented.

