9.6 Study Drug Administration

Specific instructions on administration and supplies required for administration are detailed in the Pharmacy Manual. In general, study drug will be infused through a peripheral vein IV set. The IV line will be kept open before and after the infusion with sufficient quantities of 0.9% NaCl to assure patency.

A volume of 100 mL* of placebo or AK002 at a dose of 1 mg/kg will be prepared according to the subject's body weight and administered over ≥ 4 hours on Day 1. Subsequent infusions of placebo or AK002 at a dose of 1 mg/kg or 3 mg/kg will be prepared on Day 29 (± 3), Day 57 (± 3), Day 85 (± 3), Day 113 (± 3), and Day 141 (± 3). Depending on the subject's tolerance of the first and subsequent infusions (and at the Investigator's discretion), the second infusion can be given over ≥ 3 hours, and the subsequent 4 infusions can be given over ≥ 2 hours. If the infusion is slowed or interrupted, the infusion length may exceed 4 hours but must be completed within 8 hours of preparation (prior to expiry). The same applies to the first and subsequent infusions in the OLE period of the study (for eligible subjects that choose to participate in the OLE period).

* Due to rounding of the total infusion volume by some programmable infusion pumps, an infusion of 99 mL to 101 mL will be considered a complete infusion and will not be recorded as a deviation from the study.

Prior to the first dose of study drug (12–24 hours prior to the infusion), subjects will be premedicated with oral prednisone (40 mg if body weight is <40 kg, 60 mg if body weight is ≥ 40 kg and <60 kg, or 80 mg if body weight is ≥ 60 kg). Subjects will self-administer oral prednisone 12–24 hours prior to the start of the first infusion only. As treatment assignment during the double-blind, placebo-controlled part of the study will be blinded, all eligible subjects that choose to participate in the OLE period of the study will self-administer oral prednisone premedication 12–24 hours prior to the first OLE period infusion as well.

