12.2 The Day Before the First Infusion

- 1) Confirm eligibility.
- 2) Subject will self-administer oral prednisone premedication (dose based on body weight) 12–24 hours prior to the planned infusion start time. Ensure this is documented contemporaneously (e.g., subject emails the site when taking the premedication, subject texts the Study Coordinator when taking the premedication, etc.).

12.3 Day 1 – Dose 1

- 1) Pre-Infusion:
 - a) Confirm continued eligibility.
 - b) CCI to be self-administered by the subject via their personal electronic device.
 - c) Document any changes to health status.
 - d) Document any changes to concomitant medications including confirming and documenting the date and time the subject self-administered premedication.
 - e) Document any changes to baseline diet.
 - f) Determine body weight.
 - g) Collect vital signs.

- h) Perform symptom-directed physical exam, as needed.
 - i) Collect the following samples for the central laboratory:
 - Total Serum IgE
 - CBC with differential
 - Chemistry
 - Pharmacokinetics
 - Anti-drug antibodies
 - Urinalysis, if warranted in the opinion of the Investigator or Subinvestigator
 - j) Perform urine pregnancy test (if subject is of childbearing potential).
 - k) Enter the subject's PID and body weight in the IRT system to randomize the subject.
 - l) Once the subject has been randomized in the IRT system, the pharmacist will receive an email with PID, body weight, and kit number.
 - m) The study pharmacist will prepare study drug using the weight obtained at the visit. The final combined volume of the IV bag of study drug + 0.9% NaCl will be **120 mL**.

Note: **100 mL** of the calculated dose of study drug will be administered to the subject. The extra 20 mL is to be used to prime the IV infusion line during the preparation of the IV line at the bedside or to be left over in the infusion bag.
- 2) During the Infusion of Study Drug:
- a) Infuse 100 mL of study drug over at least 4 hours using an infusion pump per the instructions and infusion rate schedule in the Administration of Investigational Product section of the Pharmacy Manual. Record the start and stop times of the infusion including any times the infusion is interrupted.
 - b) Collect vital signs 15 (\pm 5) minutes after the start of infusion.
 - c) Perform symptom-directed physical exam, as needed.

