- 32) ET visits should be conducted 28 ( $\pm 3$ ) days after the last dose of study drug or prior to this, if necessary, to ensure compliance with the visit. If a subject discontinues the study  $> 28$  days after the last dose of study drug, the ET visit should be conducted as soon as possible. If the subject is terminated after Day 29 and before Day 169, the ET visit will be performed 28 ( $\pm 3$ ) days after last dose and the ET visit will follow the Day 169 assessment schedule (including EGD with biopsy collection). If the subject is not participating in the OLE period and the ET visit occurs after Day 169, the Day 197 assessment schedule should be followed for the ET visit. See Protocol Appendix 19.12 for the OLE Period Schedule of Events for OLE period ET after Day 176.
- 33) If absolute lymphocyte and/or eosinophil counts do not recover (to normal range or baseline levels) by Day 197 (or ET), extended follow-up visits are required every 28 ( $\pm 3$ ) days to monitor blood counts until they recover. Extended follow-up visits consist of blood collection for CBC with differential and collection of AESI and SAE.
- 34) After completion of the Day 169 visit, the Investigator will evaluate whether the subject is eligible for the OLE period. If the subject is eligible, the subject will be given the option to participate in the OLE period beginning approximately 1 week after the Day 169 visit. Approximately 1 week after the Day 169 visit (on Day 176  $\pm 3$  days), eligible subjects that choose to participate in the OLE period will begin following the OLE Schedule of Events (Protocol Appendix 19.12) and will receive the first open-label AK002 infusion. For subjects participating in the OLE period, AE and concomitant medications should be collected and recorded in the AK002-014 Treatment Period database up until the start of the first open-label infusion during the Day 176 visit. This includes prednisone premedication administered prior to the Day 176 visit of the OLE period, which should be recorded in the Concomitant Medications CRF of both the AK002-014 treatment period database and the AK002-014 OLE period database.

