## 4. Definitions

### 4.1 Terminology and Definitions

**Table 2 Terminology and Definitions**

Terminology	Definition
Baseline	Baseline for non-daily assessment (e.g., laboratory tests and CCI ) is defined as the non-missing value collected most recent to and before the time of the first dose of study drug. This includes lab tests collected on Day 1 Predose as an example. Baseline DSQ score is determined from 14 days prior to the first dose.
Completer for the Study	
A subject who does not participate in the OLE period and who completes visits through the Day 197 visit or, if applicable, the last Extended Follow-Up visit after completing Day 197, will be recorded as having completed the double-blind portion of the study.
 
A subject who completes visits through the Day 169 visit and participates in the OLE period of the study will be recorded as having completed the double-blind portion of the study.
 
A subject who participates in the OLE period of the study and completes visits through the Day 372 visit or, if applicable, the last Extended Follow-Up visit after completing Day 372 will be recorded as having completed the OLE portion of the study.

Concomitant Medication	Medication collected on the Prior/Concomitant Medication CRF with end date on/after Study Day 1. Note a Prior Medication may also be a Concomitant Medication if the start date is prior to Study Day 1 and end date is on/after Study Day 1.
DSQ	Dysphagia Symptom Questionnaire: See Appendix 1 for the DSQ and the DSQ scoring algorithm.
EG/EoD Subject-Reported Outcome (PRO)	
PRO questionnaire evaluates 8 different symptoms with 10 daily questions for intensity and frequency:
 
 
• Abdominal pain intensity
 
• Nausea intensity
 
• Vomiting intensity
 
• Vomiting frequency
 
• Diarrhea intensity
 
• Diarrhea frequency
 
• Early satiety intensity
 
• Loss of appetite intensity
 
• Bloating intensity
 
• Abdominal cramping intensity
 
 
Each intensity evaluation is scored on a scale of 0=none to 10=worst possible.

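### Table 14.1.8.2 mixes the open-label prednisone premedication with true on-study steroid use, because the SAP classes medications by date alone

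*SAP*

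**What the plan says.** **Who takes the dose.** Under Protocol Section 9.6, "all eligible subjects that choose to participate in the OLE period of the study will self-administer oral prednisone premedication" 12 to 24 hours before their first open-label infusion. This applies to all three arms because the blind is still in place.

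**Where it is recorded.** Protocol Section 8 (repeated in 11.3.1) says "concomitant medications should be recorded in the AK002-014 treatment period database up until the first open-label dose is administered during the Day 176 visit". The premedication falls before that point. Note 34 to SAP Table 1 is explicit: "This includes prednisone premedication administered prior to the Day 176 visit of the OLE period, which should be recorded in the Concomitant Medications CRF", and it names both the treatment-period and the open-label databases.

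**How it is classed.** SAP Table 2 defines a concomitant medication as "Medication collected on the Prior/Concomitant Medication CRF with end date on/after Study Day 1". Section 6.10.2 says the same in words: "medications taken on or after Study Day 1 will be considered as concomitant medications". A newly initiated medication is any with a start date on or after Day 1. None of these definitions has an upper date or a premedication exclusion.

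**How it is counted.** Section 6.10.2 tabulates subjects by ATC4 class and preferred term, once per term. Appendix 3 lists the output as Table 14.1.8.2, on the Safety population.

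**What the SAP does elsewhere.** In Appendix 2, the intercurrent-event rule for corticosteroids above 10 mg/day exempts pre-infusion prophylaxis. The medication tables have no matching rule.

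**The concern.** Systemic corticosteroid is the rescue drug in this trial and a prohibited medication above 10 mg/day, so a reader will look for its use by arm. Protocol Section 6.1 also lists "Changes in concomitant medications beginning on or after the first infusion of study drug" among the safety endpoints. If the prednisone row is filled largely by a dose that every open-label entrant takes after the Week 24 assessment, two things can happen. A real difference between arms in steroid use is diluted. And if roll-over differs by arm, for instance because subjects who tolerated study drug poorly are barred from the open-label period (Protocol 19.12.3.2), the row can show a difference that has nothing to do with steroid use under double-blind treatment.

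**Working it through.** **Step 1: is the dose inside the table's definition?** The first open-label infusion is on Day 176 ±3, that is Days 173 to 179. Premedication the day before falls on Days 172 to 178. The start and end dates are after Day 1, and the record is in the treatment-period database. It therefore meets the definitions of both concomitant and newly initiated medication.

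The premedication for the first double-blind infusion is different: "Subject will self-administer oral prednisone premedication (dose based on body weight) 12–24 hours prior to the planned infusion start time". That places it on the day before Day 1, so it is a prior medication only.

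**Step 2: does it touch the co-primaries?** Week 24 ends on Day 24 × 7 = 168. On the target schedule the dose comes after Weeks 23–24 and after the Day 169 endoscopy. With the ±7 day tolerance for open-label visits, the extreme is Day 169 − 1 = 168. Even then the prophylaxis exemption in SAP Appendix 2 prevents it from being an intercurrent event.

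**Step 3: how many subjects?** The inputs are:

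- Dropout of 14% (SAP 3.6). Its use in the plan reproduces: 86 / (1 − 0.14) = 100 per arm, as stated.
- Open-label uptake among completers, u. The documents do not give it. The only proxy is the more than 90% who continued from the sponsor's Phase 2 study (Protocol 2.3), so u is varied.

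The share of an arm showing prednisone only because of roll-over is s = 0.86 × u.

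For dilution, take an assumed true use of 5% on AK002 and 15% on placebo, independent of roll-over and coded as prednisone. The displayed share is 1 − (1 − s)(1 − true use), so a 10-point difference shrinks to (1 − s) × 10.

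| Uptake u | s | 10-point difference appears as |
|---|---|---|
| 50% | 43.0% | 5.7 points |
| 70% | 60.2% | 4.0 points (62.2% vs 66.2%) |
| 90% | 77.4% | 2.3 points (78.5% vs 80.8%) |
| 100% | 86.0% | 1.4 points |

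More than half of an arm is affected only if u exceeds 0.50 / 0.86 = 58.1%.

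**Step 4: unequal roll-over.** If u were 75% on AK002 and 90% on placebo (assumed), the row would read 0.86 × 0.75 = 64.5% against 0.86 × 0.90 = 77.4%. That is a gap of 12.9 points with no other steroid use in either arm.

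**Step 5: is true use summarised by arm elsewhere?** Table 14.1.15 counts intercurrent events by arm. SAP 4.2.4 names use of prohibited or rescue medication as such an event, but refers to Appendix 2 for the detail. Appendix 2 counts corticosteroids above 10 mg/day only when started from Week 21 to the end of Week 24, so a course begun and finished before Week 21 is not counted. Major protocol deviations, which may include prohibited medication, are tabulated by arm only if numbers warrant (SAP 6.3). Appendix 3 lists no rescue-medication table. For those earlier courses, the by-arm summary rests on Table 14.1.8.2 and a conditional deviation table.

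**The case against.** The strongest reply is that this concerns one row, and its class total, in one descriptive table. No formal inference is made on safety data. SAP 6.10.2 itself requires a medication listing with study day and a separate listing of subjects who received prohibited medications. Protocol 11.3.1 requires rescue treatment to be marked as such on the eCRF. A reader might infer that true steroid use is hidden; the documents do not support that, because these sources still show it subject by subject. This part of the reply stands.

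It can also be said that the SAP's own safety endpoint (Section 2.4) is narrower than the protocol's, being limited to changes in concomitant medication due to adverse events, which premedication is not. That is fair and weakens the endpoint argument. Table 14.1.8.2 is still planned for all concomitant medications.

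Third, the provisional-lock analysis is described as covering data through Day 169, which would drop nearly all of these records. The SAP does not say that this limit applies to the medication table, and the final lock exists to analyse later safety data, so the point is unresolved.

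Finally, rescue may be a swallowed topical steroid, which could carry its own preferred term. The dilution figures apply only to use coded in the same row.

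**Conclusion.** The point holds as a reporting flaw that should be corrected. The stated definitions, applied as written, put a roll-over procedure into the same row as on-study prednisone use. The share of each arm affected is 43% at 50% uptake, 60% at 70% and 77% at 90%, given 14% dropout. Uptake is an assumption throughout, and so are the 5% vs 15% contrast and the unequal roll-over example.

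Three stronger readings are not supported:

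- **That most subjects in every arm will show on-study steroid use.** This needs uptake above 58.1% of completers. That is plausible from Phase 2 but is not stated for this trial.
- **That the co-primary results are confounded by this record.** The timing and the prophylaxis exemption rule that out.
- **That the prednisone taken before the first double-blind infusion spoils the prior-medication table to the same degree.** It is correctly a prior medication and is given alike in all arms. Oral steroids within 8 weeks of screening are an exclusion, so there is little prior use to mask beyond the stable low dose that Protocol 8.2 allows.

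**What to change.** In SAP Table 2 and Section 6.10.2:

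1. Flag protocol-required pre-infusion prednisone. Exclude it from the prednisone and corticosteroid rows of the concomitant and newly initiated summaries, show it in its own row by arm, and keep every record in the listing. The medication CRF already captures indication and dates (Protocol 11.3.1), so the flag can be derived.
2. For open-label entrants, end the double-blind medication period at the start of the first open-label infusion. This matches the recording rule for adverse events and medications. A cut at Day 169 would drop genuine medications, including treatment of adverse events, that belong to the treatment-period database until that infusion.

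The end date alone does not solve the problem, because the premedication precedes the infusion by 12 to 24 hours. The flag does the work. The cost is one data set flag and one SAP sentence; no data collection changes.

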### **6.11 Analysis of Primary Efficacy Endpoints**

To assist the data interpretation, all ICE will be listed with pertinent subject information (subject ID, date of last infusion, ICE start/stop day, nature of ICE [reason for treatment/study discontinuation if applicable, description of AE, description of prohibited/restricted medication]), baseline tissue eosinophil count and DSQ, and most recent tissue eosinophil count and 2-week average of DSQ).

A summary table will be created to present by treatment group number of subjects (n, %).

- Subjects with any ICE
  - Subjects by ICE category

#### **6.11.1 Analysis of the First Co-Primary Endpoint**

The first co-primary endpoint will be analyzed using the imputed data set (Section 5.4.1). Fisher's exact test (primary analysis) will be conducted comparing AK002 with placebo for the proportion of tissue eosinophil responders. Proportion of responders and the associated 95% CI will be presented for each treatment group. The between group difference (pairwise comparison with placebo) and the associated 95% CI will also be computed and presented. A sample SAS code is as follows.

```

* COMPUTE 95% EXACT CONFIDENCE INTERVAL FOR %RESPONSE FOR INDIVIDUAL
TREATMENT ;
ods output BinomialCLs=CL ;
proc freq data=ADEF ;
    table RESP / out=CNTS bin(cl=midp) ;
    by TRTAN ;
run;

* COMPUTE 95% EXACT CONFIDENCE INTERVAL AND FISHERS EXACT P-VALUE FOR
BETWEEN TREATMENT DIFFERENCE ;
ods output FishersExact=PVAL(where=(name1='XP2_FISH'))
RiskDiffCol2=DIFF(where=(row='Difference')) ;
proc freq data=ADEF ;
    table TRTPN*RESP / riskdiff(cl=exact) exact ;
run ;

```

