### 6.11.5 Sensitivity Analyses of the Second Co-Primary Endpoint

The 2 sensitivity analyses planned below are constructed based on the already imputed bi-weekly data set from Section 5.4.2. From this imputed data set, the bi-weekly DSQ is set to missing if it is derived from the daily scores collected on/after ICE event. This setting creates the monotone missing data set.

The first sensitivity analysis is based on the placebo-based pattern-mixture model for the missing data imputation under the missing not at random (MNAR) assumption. In this model, subjects from the active treatment group after the ICE are assumed to behave like the subjects from the placebo group. Their missing data are imputed using the response profile from the placebo subjects who have similar baseline covariates and prior response trajectory. The sample SAS code follows.

```
proc mi seed=135791 nimpute=10;
  class TRTMT;
  var B_EOS Age_Grp B_DSQ DSQ_W01_02 DSQ_W03_04 ... DSQ_W21_22
      DSQ_W23_24;
  monotone reg;
  mnar model(DSQ_W01_02 DSQ_W03_04 ... DSQ_W21_22 DSQ_W23_24 /
    modelobs=(TRTMT='0')); * CODE 0 IS FOR PLACEBO GROUP ;
run ;
```

The second sensitivity analysis is based on the tipping point method. In this method, the missing biweekly DSQ will be imputed with different adjustments for the active treatment subjects and placebo subjects under the MNAR assumption in which the search for a tipping point reverses the study conclusion (i.e., p-value no longer <0.05 for the treatment effect). A shift ranging from -x to +y representing different level of improvement or worsening due to ICE will be added to the imputed DSQ. An example of the SAS code follows.

```
proc mi seed=579864 nimpute=10;
  class AGE_STRAT TRTMT;
  var B_EOS B_DSQ DSQ_W01_02 DSQ_W03_04 ... DSQ_W21_22 DSQ_W23_24;
  monotone reg;
  mnar adjust(DSQ_W01_02 / adjustobs=(TRTMT='1') shift=&d1.)
    adjust(DSQ_W03_04 / adjustobs=(TRTMT='1') shift=&d1.)
    . . .
    adjust(DSQ_W21_22 / adjustobs=(TRTMT='1') shift=&d1.)
    adjust(DSQ_W23_24 / adjustobs=(TRTMT='1') shift=&d1.)
    adjust(DSQ_W01_02 / adjustobs=(TRTMT='0') shift=&d0.)
    adjust(DSQ_W03_04 / adjustobs=(TRTMT='0') shift=&d0.)
    . . .
    adjust(DSQ_W21_22 / adjustobs=(TRTMT='0') shift=&d0.)
    adjust(DSQ_W23_24 / adjustobs=(TRTMT='0') shift=&d0.);
run;
```

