#### **6.12.2 Proportion of Subjects Achieving Peak Esophageal Intraepithelial Eosinophil Count of $\leq 1$ and $< 15$ Eosinophils/hpf at Week 24**

These 2 endpoints will be analyzed using Fisher's exact test similar to the analysis for the first co-primary endpoint (Section 6.11.1).

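### In the SAP 6.11.1 sample code the per-arm intervals and the between-arm difference follow different levels of RESP, and the arm interval labelled exact is mid-P

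*SAP*

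**What the plan says.** The prose of SAP 6.11.1 is clear about what is to be reported: "Proportion of responders and the associated 95% CI will be presented for each treatment group", plus the pairwise difference from placebo with its 95% CI. SAP 4.2.6 and Protocol 4.5.6 make these same quantities the summary measure of the estimand for the first co-primary endpoint.

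The sample code that follows has two blocks.

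- **Per arm.** The comment begins "COMPUTE 95% EXACT CONFIDENCE INTERVAL FOR %RESPONSE FOR INDIVIDUAL". The call is "table RESP / out=CNTS bin(cl=midp" (closing bracket omitted here), run by treatment, and the limits are kept through "ods output BinomialCLs=CL". No LEVEL= or ORDER= option appears.
- **Between arms.** The call is "table TRTPN*RESP / riskdiff(cl=exact) exact", and the result is kept through "RiskDiffCol2=DIFF(where=(row='Difference" (closing characters omitted here), which is the column 2 table.

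Neither the SAP nor the protocol says how RESP is coded or which treatment forms row 1 of the two-way table.

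SAP 6.12.2 extends the method to the ≤1 and <15 eosinophils/hpf endpoints: "These 2 endpoints will be analyzed using Fisher's exact test similar to the analysis for the first co-primary endpoint". SAP 6.12.3 does the same for treatment responders.

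**The concern.** Both blocks use the same variable, but one reports its first level and the other its second. Run as written, they do not describe the same category. Under the most common coding, the interval printed beside each arm's responder rate would be the interval for non-response. The sign of the difference would depend on a row order that is not stated. Separately, the comment promises an exact interval and the option requests a different one.

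At stake are the reported estimates for the first co-primary endpoint and for the three secondary endpoints analysed in the same way.

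**Working it through.** **The plan's own figure.** SAP 3.6 gives 8 per group for 90% power at 90% v 10% response. Two-sided Fisher power at 0.05, by full enumeration, is 84.2% with 7 per group and 93.2% with 8, so 8 is reproduced. It is not in dispute. The 90% and 10% rates, with about 100 per arm (SAP 3.3.3, 3.6), serve below as an illustration.

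**Software behaviour assumed (not stated in the documents).** Without LEVEL=, the BINOMIAL option reports the first ordered level. RiskDiffCol2 is the second level. The difference is row 1 minus row 2.

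**Interval formulas, x responders of n, α = 0.05.**

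- Exact (Clopper-Pearson): the lower limit solves P(X ≥ x) = 0.025 and the upper solves P(X ≤ x) = 0.025.
- Mid-P: the lower limit solves P(X > x) + ½P(X = x) = 0.025 and the upper solves P(X < x) + ½P(X = x) = 0.025.

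| Count | Exact | Mid-P |
|---|---|---|
| 90/100 (response) | 82.4% to 95.1% | 82.9% to 94.8% |
| 10/100 (non-response) | 4.9% to 17.6% | 5.2% to 17.1% |

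**What the code returns with 90/100 responders on AK002 and 10/100 on placebo.**

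| RESP coding | Row 1 | AK002 arm interval describes | Column 2 difference |
|---|---|---|---|
| 0 = non-responder, 1 = responder | placebo | non-response, 5.2% to 17.1% | response, 10 − 90 = −80 points |
| 0 = non-responder, 1 = responder | AK002 | non-response, 5.2% to 17.1% | response, 90 − 10 = +80 points |
| 1 = responder, 2 = non-responder | placebo | response, 82.9% to 94.8% | non-response, 90 − 10 = +80 points |
| 1 = responder, 2 = non-responder | AK002 | response, 82.9% to 94.8% | non-response, 10 − 90 = −80 points |

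N/Y and Non-responder/Responder sort like 0/1. In the third row, placebo minus AK002 non-response equals AK002 minus placebo response. The number is the intended one and only its label is for non-response.

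The SAP shows a placebo code once, in the DSQ code of 6.11.5 ("CODE 0 IS FOR PLACEBO GROUP"), for a different variable, TRTMT. If TRTPN followed the same convention, placebo would be row 1.

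**Exact v mid-P.** At 90/100 mid-P moves the lower limit by 82.9 − 82.4 = 0.5 points and the upper by 95.1 − 94.8 = 0.3 points. At n = 100 and true rates from 0.02 to 0.98, the minimum coverage of mid-P is about 92.1% (mean 95.2%). For the exact interval the minimum is 95.0%.

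**Test.** Swapping the two RESP columns leaves the two-sided Fisher p-value unchanged.

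**The case against.** The strongest reply is that this is labelled sample code and the governing prose correctly asks for responder proportions and a comparison with placebo. The code is visibly a sketch: the two-way table is not restricted to two arms although the trial has three. A programmer would define RESP, and a 90% response beside an interval of 5% to 17% would be noticed. SAP section 7 also requires tables to be independently reprogrammed. The mid-P point can be settled by changing one word in a comment, because the prose asks only for a 95% CI.

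Much of this stands, and it limits the consequence. It does not remove the problem. The sample is the only place where the SAP specifies the interval methods for this analysis, and double programming would not catch the error if both programmers copied it.

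Three stronger readings are tempting but not supported.

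- **That no coding can make both outputs right.** With responders coded first and placebo in row 1, the arm intervals are correct and the difference has the intended value and sign, although its label is for non-response.
- **That the subgroup tables inherit the intervals.** SAP 6.11.3 specifies only Fisher's exact test by subgroup and promises no arm intervals there.
- **That arms in one table will often describe different categories.** Under 0/1 coding, an arm in which everyone responds has one level, and its interval would be for responders. At 90% response and n = 100 the chance is 0.9^100 ≈ 0.00003. For an assumed arm of 10 it is 0.9^10 ≈ 0.35 for that one arm, but the documents give no such size.

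**Conclusion.** The point holds. Run as written, the sample code reports the arm intervals and the difference for different RESP levels, and its exact label contradicts its mid-P option. Under 0/1 coding the illustrated AK002 interval would be 5.2% to 17.1% instead of 82.9% to 94.8% mid-P (82.4% to 95.1% exact), and with placebo in row 1 the difference would be −80 rather than +80 points. With responders coded first, the fault is in the label of the difference and, if AK002 is row 1, in its sign.

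The label conflict can be read directly from the SAP. The level mismatch rests on PROC FREQ defaults and on the sample being run without further options. The sizes rest on the planning rates with 100 per arm.

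A reader might infer that the success decision is at risk. It is not: the testing order in SAP 5.8 runs on p-values, which do not change. The effect is confined to reported intervals and the sign or label of the difference, for the first co-primary endpoint and the endpoints in 6.12.2 and 6.12.3. Because these are the estimand's summary measures, the code should be corrected.

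**What to change.** In SAP 6.11.1:

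1. Define RESP=1 as response and RESP=0 as non-response.
2. Name the level in the per-arm call, for example `bin(level='1' cl=exact)`.
3. Read the difference for the same level, with a stated row order that gives AK002 minus placebo, and one active arm against placebo per call. Naming the level alone is not enough, because the sign follows the row order.
4. Either request exact (Clopper-Pearson) limits or keep mid-P and relabel the interval.
5. State that the same code applies to the endpoints in 6.12.2 and 6.12.3.

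The cost is a few words of code and comment. If exact limits are chosen, the per-arm intervals become slightly wider, by 0.5 points at the lower limit and 0.3 at the upper for 90/100. No test, sample size or testing order changes.
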